13.6.4. Study Drug Administration at Home

The study drug will be applied to the Treatment Field by the subject or their dosing partner. Subjects in Cohort 1 will apply approximately 200 mg of 10%VDA-1102 each morning before 10:00 am and each evening at least 3 hours prior to bedtime. Subjects in Cohort 2 will apply approximately 200 mg of 20%VDA-1102 each morning before 10:00 am.

Cohorts 1 and 2: The morning dose should be applied before 10 am. **If a subject knows that they will perspire, shower, vigorously exercise, etc. before 10 am, application of the study drug should be delayed until completion of those activities.**

Cohort 1 only: The evening dose should be applied each day **at least 3 hours** before bedtime.

If the subject would like to shower, wash their face, shampoo their hair, etc., these should be performed prior to study drug application.

At the dosing time, the subject should check the Treatment Field in the mirror to assure it is clean and dry.

The study drug tube will be removed from the container, the tube cover unscrewed, and the study drug ointment expressed as a strip into the rectangle printed on the supplied Dosing Card.

Using a mirror, Treatment Field photograph, and/or the landmarks drawn on the Treatment Field Template, the template will be appropriately positioned on the subject's face or scalp. The subject (or dosing partner) will apply the study drug to the Treatment Field on their skin that corresponds to the 25 cm² area cut out of the template. Subjects (or their dosing partners) will apply the study drug with one finger to the center of the Treatment Field and spread the ointment evenly over the entire field. The Treatment Field will **not** be occluded. The subject will remove the Treatment Field Template from their face. With the same finger, the subject will spread ointment at the periphery of the Treatment Field approximately ¼ inch beyond the Treatment Field perimeter to ensure that the whole Treatment Field was covered with study drug.

After each study drug application, the subject's hands should be very carefully washed with warm water and soap.

The subject will be instructed not to wet or touch the Treatment Field. Subjects should not perform activities that might cause wetting or excessive sweating of the Treatment Field, for approximately 6 hours after dosing.

After each dosing, the Dosing Diary must be completed.

13.7. Study Drug Accountability and Dosing Compliance

13.7.1. Study Drug Site Accountability

Study sites will be asked to acknowledge receipt of the study drugs on the day of arrival at the site. The site pharmacist and/or the assigned site personnel will be responsible for drug inventory. A drug inventory record should be maintained by the person responsible for dispensing the study drug to the subject. This should record which supplies arrived at the site and which container(s) is issued to each subject. The Sponsor should be notified of details of any supplies which are inadvertently damaged. Details of any supplies which are inadvertently damaged or unaccountable for any reason should be documented on the drug inventory record, which will be collected at the end of the study.

All study drug will be inventoried by the monitor during and at the conclusion of the study. Secure disposal or return of unused supplies to the Sponsor at the end of the study will be arranged. Sufficient study drug will be given to each subject to allow for proper dosing between site visits.

13.7.2. Study Drug Accountability and Dosing Compliance

Study drug distributed to each subject and returned by each subject will be documented in the Drug Accountability Log.

Dosing cards will be distributed and collected with study drug. Subjects will complete a Dosing Diary with the date and time of each dosing. Missed doses will be recorded. Dosing cards will be used to assess subject compliance.

13.7.3. Study Drug Weighing

Each new (unused) study drug tube will be weighed before the first dose is dispensed. As part of study drug accountability, study tubes returned by the subjects at Weeks 4, 8, and 12 will be weighed. Study drug weights will be recorded and these data will be used to assess subject compliance.

14. CONCOMITANT MEDICATION

Any prescription or non-prescription medication, alternative medication, herbal product, homeopathic substance, etc. that the subject receives while they are enrolled in the trial or that was taken within 2 months of Screening will be referred to as a Concomitant Medication. The Investigator is to record the use of all concomitant medications, both prescribed and over-the-counter, in the subject medical record.

Subjects should be advised against taking any new medication, both prescribed and over-the-counter, without consulting the Investigator, unless the new medication is urgently required for emergency use. Subjects taking medication other than those listed as prohibited in Section 12.9.1 may continue taking their routine medications and vitamins so long as they have been taking them for at least 2 months prior to Screening with no change in dose or dosing interval.

At Screening and Day 1 Pre-Dose Visits, the study site personnel will review each subject's concomitant medications to ensure that subjects are not taking any prohibited medications listed in Section 12.9.1.

The Investigator and his designees are obligated to ensure the well-being of all subjects during this study. Consequently, no medication or treatment should be withheld from a subject requiring medical intervention. This may include treatments received by the subject prior to enrollment as well as in response to any new medical conditions that developed during the study. The Investigator (or designee) must inform a subject when concomitant medical intervention or treatment is indicated and report this in the appropriate section of the CRF.

15. ADVERSE EVENTS

15.1. Adverse Event Definitions

15.1.1. General

An AE is any untoward medical occurrence which does not necessarily have to have a causal relationship with the pharmaceutical product treatment. Any worsening of the subject's disease under study or other medical conditions will also be considered to be an AE, unless it is within the normal range of disease fluctuation for that subject.

Abnormal clinically significant changes in physical examination or vital signs should be recorded as AEs.

15.1.2. Local Skin Reactions

In this trial Local Skin Reactions (LSRs) will not be recorded as AEs unless they (a) require treatment with a prescribed medication; (b) extend >2 centimeters beyond the border of the Treatment Field; or (c) require a study drug dose adjustment.

15.1.3. Laboratory and ECG Data

Abnormal clinical laboratory or ECG findings should be reported as an AE are as follows:

1. Test result is associated with accompanying symptoms;
2. Test result requires additional diagnostic testing or medical/surgical intervention;
3. Test result leads to a change in study dosing, discontinuation from the study, initiation of a prescription medication, or surgical intervention; and
4. Test result leads to any of the outcomes included in the definition of a SAE.

If such an event occurs, the test should be repeated within approximately 7 days to confirm the finding and appropriately monitored. The mere repetition of an abnormal test, in the absence of any of the above conditions, does not fulfil Condition 2 above for reporting as an AE. Any abnormal test result that is determined to be an error does not require reporting as an AE.

15.1.4. Miscellaneous Definitions

Treatment Emergent Adverse Events (TEAEs) are AEs that occur *de novo* or worsen following the initiation of study treatment.

Surgical procedures themselves are not AEs; they are therapeutic measures taken due to an AE and they should be documented as such.

Planned hospital admissions documented in the subject's medical record prior to enrolment and study-related procedures are also not to be reported as AEs.

Overdoses of the study drug will not be reported as an AE. However, any AEs or SAEs, as defined in Section 15, associated with an overdose will be reported as such.

15.2. Clarification of the Difference between “Severe” and “Serious”

Severity describes the intensity of an event, irrespective of its medical significance (such as severe headache). This is not the same as seriousness, which is based on regulatory definitions. Seriousness (not severity) defines SAE reporting obligations. The severity of all AEs will be graded on a 3-point scale (mild, moderate, severe) and reported in detail on the CRF.

- Mild: Discomfort noticed but no disruption of normal daily activity.
- Moderate: Discomfort sufficient to reduce or affect daily activity.
- Severe: Inability to work or perform normal daily activity.

15.3. AE Reporting

Specific instructions regarding the reporting of AEs, including start and stop dates, relationship to study drug, outcomes, expectedness, etc. will be detailed in the Safety Monitoring Plan.

15.4. Relationship to Study Treatments

“Causality” refers to the relationship of the AE to the study drug. The investigator must include assessment of causality (whether there is a reasonable possibility the drug caused the event) for each AE. Causality will be categorized according to the following criteria:

- **Not Related:** There is no medical evidence to suggest that the AE may be related to study drug usage and other causes are much more likely.
- **Unlikely Related:** There is no medical evidence to suggest that the AE may be related to study drug usage, but a relationship cannot be completely ruled out. There are other more likely causes.
- **Possibly Related:** There is weak medical evidence to suggest that the AE may be related to study drug usage and a relationship cannot be completely ruled out.
- **Likely Related:** There is good medical evidence to suggest that the AE may be related to study drug usage but other causes cannot be ruled out completely.
- **Related:** There is a strong and convincing medical evidence to suggest that the AE is related to study drug usage and other possible causes are highly unlikely.

15.5. Follow-up of Adverse Events

All AE related symptoms and/or signs will be followed until there is a return to the baseline status, all associated parameters have returned to normal (or are no longer considered clinically significant), stabilized, or no further improvement is anticipated. Follow-up is mandatory, irrespective of causal relationship to the study drug(s). SAEs will be monitored until resolution or stabilized as medically indicated. Any subject who has received at least 1 dose of the study drug and has experienced an AE that has not resolved or stabilized, may be invited to attend and unscheduled visits. Subjects with AEs that have not resolved or stabilized should be followed until resolution of the AE or for a minimum of 30 days after the subject’s last application of the study medication.

16. SERIOUS ADVERSE EVENTS

16.1. Definition

An SAE is any AE that, at any dose, results in at least one of the following outcomes:

1. Death. Death is an outcome, not an event. Where the cause of death is uncertain, the reported SAE should be the same as the term on the subject's death certificate.
2. Life-threatening. Life-threatening means that the subject was at immediate risk of death at the time of the SAE; it does not refer to an SAE that hypothetically might have caused death if it were more severe.
3. Requires or prolongs inpatient hospitalization.
4. Persistent or significant disability or incapacity. "Persistent or significant disability or incapacity" means that there is a substantial disruption of a person's ability to carry out normal life functions.
5. Congenital anomaly or birth defect.
6. Medically serious event based upon appropriate medical judgment. Examples of such medical events include allergic bronchospasm requiring intensive treatment in an emergency room or at home, blood dyscrasias or convulsions that do not result in inpatient hospitalization, or the development of drug dependency or drug abuse.

16.2. Reporting of Serious Adverse Events

Full details of SAE reporting will be based on the ICH guidelines for reporting SAEs and will appear in the study Safety Monitoring Plan.

If the AE is serious, the Investigator must complete an SAE Report form, in addition to the AE page in the CRF. In addition, when a non-serious event becomes serious, details must be forwarded, within 24 hours of Investigator awareness that an AE has become serious, to the Sponsor or designee on an SAE Report form, with the date of the seriousness upgrade as the SAE start date.

The SAE Report Form must be completed in accordance with instructions provided by the Sponsor or designee. The completed form must be emailed to [name], the Study Safety Monitor, within 24 hours of discovery of the SAE.

The initial report must be as complete as possible, including details of the current illness and the SAE, and an assessment of the causal relationship between the event and the investigational product(s) or the study procedures.

Information not available at the time of the initial report (e.g., an end date for the AE or laboratory values received after the report) must be documented as a follow-up on the SAE Report form.

Any SAE, whether or not related to the study treatment, must be reported within 24 hours to the Study Medical Monitor and the CRO responsible for the site. The following contact and

communication methods may be used. The Medical Monitor and CRO will confirm receipt upon receiving the notification.

[name], Study Medical Monitor (Sponsor)

Telephone (mobile): [name]

E-mail: [contact]

[name], Project Manager (Therapeutics, Inc.)

Telephone (mobile): [name]

E-mail: [contact]

Office: [name]

[contact]

If, for any reason, the Investigator cannot notify the Study Safety Monitor via the appropriate form or if the Investigator suspects that using this method will delay the notification (e.g., during a holiday period), the Investigator must verbally notify the Sponsor Medical Monitor (or designee) via telephone. The SAE Report form must still be relayed at the earliest possible opportunity. SAEs must be reported to the IRB according to IRB guidelines.

All ancillary documentation (e.g. discharge letters, laboratory reports and consultations) must be sent to the Sponsor or designee. In the event of an SAE resulting in death, post-mortem reports should be routinely sent to the Sponsor or designee.

All subjects with SAEs must be followed-up for outcome.

17. STATISTICAL PLAN

17.1. Sample Size Rationale and Justification

The study is designed to evaluate the efficacy, safety, and tolerability of topical VDA-1102 ointment in subjects with actinic keratosis. Approximately 150 subjects will be enrolled in this 2-cohort clinical trial. In each cohort, approximately 75 subjects will be enrolled in order to complete each cohort with safety and efficacy data from at least 70 subjects who received study drug. Considering the results from a previous Phase 2 parallel, randomized, placebo-controlled study with a sample size of 29 to 32 subjects per treatment group, this sample size is considered adequate to evaluate the stated objectives. A formal sample size calculation was not performed.

17.2. Statistical analysis

All measured variables and derived parameters will be listed individually and, if appropriate, tabulated by descriptive statistics. Data will be summarized by cohort and visit, if appropriate. Unless stated otherwise, the term “descriptive statistics” refers to number of subjects (n), mean, median, standard deviation (SD), minimum, and maximum for continuous data and frequencies and percentages for categorical data. The data will be analyzed using the SAS[®] version 9.4 or higher (SAS Institute, Cary North Carolina). Details of all statistical analyses to be performed will be included in the Statistical Analysis Plan (SAP).

17.3. Secondary Efficacy Analyses

17.3.1. Primary Efficacy Analyses

The proportion of subjects achieving complete clearance of AK lesions within their Treatment Field will be summarized by cohort and visit. The 95% confidence interval for the percentage will be calculated using the Clopper-Pearson method for binomial proportions. The analysis will be conducted on the modified Intent-to-Treat (mITT) population, mITT Face (mITT-Face) subpopulation, Per Protocol population (PP), and PP Face (PP-Face) subpopulation.

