Study Design 
This Phase 2 clinical trial is a 3-part, open-label, multi-center study involving a non-occluded, daily topical dermal application of 1 of 2 strengths of VDA-1102 ointment for approximately 12 weeks (84 days) to an initial 2 cohorts of subjects. The first 40 eligible subjects will be enrolled into Cohort 1 (Part A). Cohort 1 subjects will be assigned to receive approximately 200 mg of 10% VDA-1102 twice-daily (BID). Once approximately 40 subjects have been enrolled in Cohort 1, Cohort 1 will be closed to enrollment and Cohort 2 (Part B) will be opened for enrollment. Cohort 2 subjects will be assigned to receive approximately 200 mg of 20% VDA-1102 once-daily (QD). Once approximately 40 subjects have been enrolled in Cohort 2, an additional 70 subjects will be randomly assigned to Cohort 1 or Cohort 2 (Part C) in a 1:1 ratio.
 
To qualify for the study, subjects aged 18 (inclusive) or older must have signed informed consent and met the study enrollment criteria that include having 4-8 actinic keratosis (AK) lesions within an approximate 25 cm² area on the cheek, forehead, or hairless scalp (the "Treatment Field").
	

Parts A, B, and C of this clinical trial will each include the same 3 study periods, a Screening Period (Day -21 through Day 1 Pre-Dose), a Treatment Period (Day 1 Dosing through Week 12), and a Post-Treatment Follow-Up Period (Week 13 through Week 16).

During the **Screening Visit** (up to 21 days pre-dose) subjects who have given written informed consent will undergo safety assessments, Treatment Field identification, and other qualifying procedures.

At the **Day 1 Pre-Dose Visit**, eligible subjects will return to the investigative site for baseline assessments as well as final eligibility screening. Subjects who continue to meet the enrollment criteria will be enrolled and will continue to the Day 1 Dosing Visit. The number of AK lesions within the Treatment Field will be recorded.

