- Percentage of subjects achieving partial ($\geq 75\%$) clearance of AK lesions within their Treatment Field on Week 16
- Percentage of subjects with facial Treatment Fields achieving partial ($\geq 75\%$) clearance of AK lesions on Week 16
- Change from baseline in the number of AK lesions in the Treatment Field of each subject by Weeks 16
- Change from baseline in the number of facial AK lesions in the Treatment Field of each subject by Weeks 16

Safety Endpoints:

- AEs, clinical laboratory parameters, vital signs, physical examinations, Local Skin Reaction (LSR) Scores, electrocardiograms, and drug exposure.

Statistical Analyses:***Sample Size***

The study is designed to evaluate the efficacy, safety, and tolerability of topical VDA-1102 ointment in subjects with actinic keratosis. Approximately 150 subjects will be enrolled in this 2-cohort clinical trial. In each cohort, approximately 75 eligible subjects will be enrolled in order to complete each cohort with safety and efficacy data from at least 70 subjects who received study drug. Considering the results from a previous Phase 2 parallel, randomized, placebo-controlled study with a sample size of 29 to 32 subjects per treatment group, this sample size is considered adequate to evaluate the stated objectives. A formal sample size calculation was not performed.

Efficacy Analyses

Efficacy endpoints will be summarized by cohort and visit on the modified Intent-to-Treat (mITT) population and Per Protocol (PP) population, as well as on pre-defined subgroups of the modified Intent-to-Treat population and Per Protocol population including subjects whose Treatment Field was on their face (i.e., cheek or forehead, not scalp).

Given that the study does not contain a control arm, formal statistical analyses of the efficacy data are not planned.

Safety Analysis

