5.6.4. Study Design Rationale

The results from the Phase 2a (VDA-CP-03; Section 5.5.2) clinical trial support the safety and tolerability of 200 mg of 10% VDA-1102 ointment when applied once-daily for 4 weeks (28 days), but the efficacy was moderate. In the completed Cohort 1 of the ongoing Phase 1B trial (VDA-CP-04; Section 5.5.3) subjects treated with 10% VDA-1102 twice-daily for 8 weeks the efficacy was improved, while safety and tolerability were maintained. These studies suggest that higher study drug concentrations, more frequent dosing, and/or a longer treatment duration are likely to improve efficacy. The non-clinical and clinical data support the safety of this approach as well.

In Cohort 1 (**Part A**) of the current study 40 subjects will apply approximately 200 mg of 10% VDA-1102 twice-daily, the same dose applied in Cohort 1 of trial VDA-CP-04. However, subjects enrolled in the current study (VDA-CP-05) will apply the study drug to their Treatment Field for 12 weeks instead of 8 weeks.

Once approximately 40 subjects have been enrolled in Cohort 1 (Part A), this cohort will be closed to enrollment and Cohort 2 (Part B) will be opened for enrollment.

The reason for the initial split into Part A and Part B is due to the drug product manufacturer's schedule (i.e., drug supply).

In Cohort 2 (**Part B**) approximately 40 subjects will apply approximately 200 mg of 20% VDA-1102 once-daily to their Treatment Field for 12 weeks.

Following completion of enrollment of approximately 40 subjects into Cohort 2 (Part B), **Part C** will be opened to enrollment wherein 70 subjects will be randomized in a 1:1 ratio to either Cohort 1 or Cohort 2. Thus, the trial will close with a total of approximately 75 subjects in each cohort.

The goals and rationale of this open-label, dose-escalation trial are to assess the tolerance, safety, and efficacy of two different dosing strategies for VDA-1102 ointment. The results of this study will be applied to the study design and dose selection for the pivotal Phase 3 trials.

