5.7. Dose and Posology Justification

Vidac is assessing the dose-response curve and therapeutic index of VDA-1102 ointment in AK subjects to further determine the most appropriate treatment parameters to support a potential Phase 3 study. The Phase 2a trial (VDA-CP-03) involved once-daily 200 mg application of 10% VDA-1102 to a 25cm² Treatment Field on the face or balding scalp of subjects with AK for 4 weeks. The study drug was well-tolerated with hardly any LSRs reported. Neither VDA-1102 nor its major metabolite JA was detected in the plasma of treated subjects. The reduction in the number of AK lesions in this short, proof-of-concept trial was modest.

In the completed Cohort 1 of the ongoing dose-ranging Study VDA-CP-04, 5 AK subjects applied 200 mg of 10% VDA-1102 twice-daily for 8 weeks to a 25cm² Treatment Field on the face or balding scalp. In this small study, the reduction in AK lesions was considerably better (74%) than in the Phase 2a trial (32%) and no systemic exposure was found for VDA-1102 or its major metabolite, supporting an even longer (e.g., 12 week) treatment period in order to obtain clinically significant complete clearance.

The goals of the current study (VDA-CP-05) are to evaluate efficacy, safety, and tolerability of the same total daily dose of VDA-1102 already tested in a previous clinical study (VDA-CP-05). This total daily dose (1.67 mg/kg/day) will be given either as a divided dose of 10% VDA-1102 BID (Cohort 1) or a single dose of 20% VDA-1102 QD (Cohort 2) for a 12-week treatment period. This dose (1.67 mg/kg/day) is close to 20-fold lower than the HED of the NOAEL dose determined in the 13-week dermal toxicity study in minipigs (32 mg/kg/day) and is close to 30-fold lower than the HED of the NOAEL dose determined in the oral 13-week toxicology study in rats (48 mg/kg/day).

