17.3.2. Secondary Efficacy Analyses

The proportion of subjects achieving partial ($\geq 75\%$) clearance of AK lesions within their Treatment Field will be summarized by cohort and visit. The 95% confidence interval for the percentage will be calculated using the Clopper-Pearson method for binomial proportions.

The number of facial AK lesions in the Treatment Field, change from baseline values, and percent change from baseline values will be summarized by cohort and visit.

These analyses will be conducted on the modified Intent-to-Treat (mITT) population, mITT Face (mITT-Face) subpopulation, Per Protocol population (PP), and PP Face (PP-Face) subpopulation.

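### Each cohort pools sequential non-randomized subjects with randomized ones, and the text provides neither a display by Part nor a regimen difference in randomized Part C

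*Combined protocol and SAP*

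**What the plan says.** Enrolment runs in three steps (Synopsis, Study Design; Sections 5.6.4 and 12.1.2). Part A takes the first 40 subjects, all into Cohort 1 (10% BID), and closes. Part B then takes about 40, all into Cohort 2 (20% QD). Neither step is randomized. The stated cause is supply: "The reason for the initial split into Part A and Part B is due to the drug product" manufacturer's schedule. Part C follows: "Once approximately 40 subjects have been enrolled in Cohort 2, an additional 70 subjects will be randomly assigned" to the two cohorts, 1:1.

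The efficacy displays do not separate these steps:
- Synopsis, Efficacy Analyses: "Efficacy endpoints will be summarized by cohort and visit on the modified Intent-to-Treat (mITT) population and Per Protocol (PP) population", and on subgroups that include facial Treatment Fields.
- Section 17.3.1 (primary): "The proportion of subjects achieving complete clearance of AK lesions within their Treatment Field will be summarized by cohort and visit", with a Clopper-Pearson 95% interval on each percentage.
- Section 17.3.2 (secondary): lesion counts, "change from baseline values, and percent change from baseline values will be summarized by cohort and visit".
- Section 17.10: cohort comparability is described by demographics such as age, gender and country. Part, baseline lesion count and field location are not named.

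On the use of the results, Section 5.6.4 gives the aim as to "assess the tolerance, safety, and efficacy of two different dosing strategies for VDA-1102 ointment" and adds: "The results of this study will be applied to the study design and dose selection for the pivotal Phase 3 trials". Section 5.7 describes the programme as intended "to further determine the most appropriate treatment parameters to support a potential Phase 3 study".

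**The concern.** More than half of each cohort received its regimen because of when the subject enrolled. Across those subjects, regimen and enrolment period cannot be told apart. Anything that moved between the two periods would appear as a difference between regimens: case mix, the mix of active sites, season, or how open-label assessors count lesions.

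The two cohort percentages are the only efficacy figures the text offers on the two dosing strategies. With Phase 3 dose selection as the stated use, they will foreseeably be set side by side. Part C holds a concurrent randomized comparison free of this mixing, but the protocol text does not say it will be shown. If the choice between Part C and pooled data is left until results are known, it can be influenced by them.

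**Working it through.** **Inputs from the documents.** Part A 40, Part B about 40, Part C 70 at 1:1, about 75 per cohort and 150 in total (Synopsis; Sections 5.6.4 and 17.1). Study duration about 12 months and at most 143 days per subject (Synopsis). Facial share about 75% in the earlier Phase 2 study (Section 5.5.2).

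**Assumptions.** Clearance rates of 10%, 30% and 50%, the same in both cohorts for standard errors. Period shifts of 5 and 10 percentage points. The documents give neither quantity.

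**The plan's own figures.** 40 + 70/2 = 75 per cohort and 40 + 40 + 70 = 150. Both reproduce.

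**Weight on the period shift.** Let d be the true regimen difference (Cohort 1 minus Cohort 2), and let pA, pB and pC be additive period levels. The all-subject difference is

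[40(d + pA) + 35(d + pC)]/75 − [40 pB + 35 pC]/75 = d + (40/75)(pA − pB).

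The Part C level cancels, so the weight is 40/75 = 0.533. In Part C alone the weight is zero.

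- With 70 completers per cohort, the weight is 35/70 = 0.500 if all 5 losses fall in Parts A and B, and 40/70 = 0.571 if all fall in Part C.
- With A = B between 38 and 42 and cohorts held at 75, it runs from 38/75 = 0.507 to 42/75 = 0.560.
- If A and B differ in size, pC no longer cancels completely.

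**Bias.** Shift 5: 0.533 × 5 = 2.7 points. Shift 10: 0.533 × 10 = 5.3 points.

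**Precision and coverage.** SE = 100·√(2p(1−p)/n) and half-width = 1.96·SE. Coverage of a nominal 95% interval is Φ(1.96 − b) − Φ(−1.96 − b), with b = bias/SE for 75 v 75. The break-even shift, above which Part C has the lower root-mean-square error, is √(SE₃₅² − SE₇₅²)/0.533.

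| Clearance | SE, 75 v 75 | SE, 35 v 35 | Half-width, all | Half-width, Part C | Coverage, shift 5 | Coverage, shift 10 | Break-even shift |
|---|---|---|---|---|---|---|---|
| 10% | 4.90 | 7.17 | 9.6 | 14.1 | 91.5% | 80.7% | 9.8 |
| 30% | 7.48 | 10.95 | 14.7 | 21.5 | 93.5% | 89.0% | 15.0 |
| 50% | 8.16 | 11.95 | 16.0 | 23.4 | 93.8% | 90.0% | 16.4 |

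At 30%, all-subject root-mean-square error is √(7.48² + 2.67²) = 7.9 for shift 5 and √(7.48² + 5.33²) = 9.2 for shift 10. For Part C it is 10.95.

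**Facial subset of Part C.** 0.75 × 35 ≈ 26 per arm. SE at 30% is 12.71 and the half-width 24.9 points.

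**Can Part columns detect a shift?** Comparing the A-minus-B difference with the Part C difference at 30% has half-width 196·√(2 × 0.3 × 0.7 × (1/40 + 1/35)) = 29.4 points (19.2 at 10%, 32.1 at 50%). The columns would disclose a large shift but could not rule one out.

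**How far apart are Parts A and B?** Assuming uniform accrual over 365 − 143 = 222 days, 40 subjects take 222 × 40/150 = 59 days. The two Parts are then centred about 59 days apart, or more if there is a supply gap.

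**The case against.** The strongest reply is that the protocol makes no such comparison. Its objectives and endpoints (Sections 6 and 8) are cohort percentages and lesion changes, the intervals are one-sample, and the Synopsis plans no formal efficacy analysis. Section 12.1.2 gives Part C randomization a non-comparative purpose: to enlarge both cohorts equally. This stands, and it is why the point is not an error in a stated analysis. It does not remove the foreseeable side-by-side reading. Nor does the lack of a control arm, the reason given in the Synopsis, prevent describing a randomized contrast between two regimens.

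Second, Section 17.2 leaves analysis details to a SAP, and the Synopsis subgroup list is open-ended. The SAP text was not supplied, so the gap is established for the protocol text only.

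Third, the remedy is imprecise. At 30% clearance, pooling is the more accurate choice unless the shift exceeds 15 points. Nothing in the documents suggests a shift that large, and periods and procedures are common to the Parts (Sections 7.1 and 7.2). This stands too. It argues for showing both results, not for replacing the cohort totals.

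Fourth, 0.53 rests on approximate Part sizes. Allocation is to be balanced across all enrolled subjects (Section 12.1.2), and Section 9.4 allows replacement. The range above covers modest departures. For the facial endpoint the weight depends on the facial share in each Part, which is not given.

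**Conclusion.** The concern holds as a reporting gap in the protocol text. Read side by side, the cohort results carry about 0.53 (roughly 0.50 to 0.57 under plausible losses) of any shift between the Part A and Part B enrolment periods, and the comparison free of that shift is not named for display. The weight assumes additive period effects and equal Part A and Part B sizes. The shift itself has unknown size and direction; at an assumed 5 points the effect on coverage is slight at 30% clearance, and at 10 points it is material. Part C does not remove bias from open-label assessment (Section 12.1.1). Given the stated use for Phase 3 dose selection and the low cost, the change is worth making before results are seen.

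**What to change.** Add to Section 17.3.1, or cross-reference the SAP if it already does this:

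> Efficacy tables show Part A or B and Part C columns within each cohort beside the cohort total. For Week 16 complete clearance (mITT and mITT-Face), the Cohort 1 minus Cohort 2 difference with a Newcombe 95% CI is also estimated descriptively in the randomized Part C subjects. Any all-subject or Part A versus Part B comparison is labelled descriptive and open to enrolment-period bias.

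Keep the cohort totals and do not name a single main contrast. In Section 17.10, tabulate baseline AK count and Treatment Field location by cohort and Part.

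The cost is a few sentences and extra table columns, with no new data or subjects. The downside is imprecision. At 30% clearance the Newcombe half-width is 20.8 points in Part C against 14.4 for all subjects. A single-Part column is also loose: 12/40 has a Clopper-Pearson interval of 16.6% to 46.5%.
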